### Qualitative Interview on Moral Injury Data Collection (Objective 3)

We will conduct in-depth interviews, 20-40 (with a maximum of 40 HCW), from intervention sites. Qualitative interviews will focus on assessing HCWs' perspectives on the presence of moral injury/ moral trauma among HCW in this area, how the experience of moral injury/ moral trauma may impact HCWs' work and/or wellness, and what services or interventions may be supportive for those experiencing or at risk for experiencing moral injury/ moral trauma.

### **Table 4: Measures (HCW)**

*Measures collected via surveys with HCW at baseline, and 1 month after the last session (6 months after baseline in the control site):*

- (1) Resilience
- (2) HIV Stigma
- (4) Burnout
- (5) Depersonalization
- (6) Moral Injury Questionnaire\*70
- (7) Depression #
- (8) Anxiety#
- (9) Suicide Screening#

*[\*Only to be done at baseline  
#Only to be done at endline]*

## **Procedures for Patients living with HIV**

### *Procedures for PLHIV who have agreed to participate in the survey.*

Survey administration with PLHIV participants enrolled in the study will be completed at two time points: one at baseline (i.e., study initiation) and one at endline (i.e., at 6-7 months after study initiation), including sociodemographic data and three questionnaire components related to: Medical Mistrust, Patient Satisfaction, and Perceived stigma from Health care Providers (**Appendix 2**). The survey will be done at the health facility or at a location suggested by the participant as per the participant's preference, at a location where privacy can be guaranteed as much as possible with the support from a surveyor who is fluent in Echuabo (local language). Participants may be recruited for more than one survey time point, however, different PLHIV participants can be recruited at the two time points. Participants will be requested to allow the use of the Moral Trauma Protocol, Version 1.3; PI: [name], 27 September 2024

of a subset of data related to their ART medication pick-up history for the past 6 months will be collected from their medical records for use in analyzing the survey data (**Appendix 10**). These data will be extracted from the electronic patient tracking system OpenMRS™, which stores clinical information from the medical records of PLHIV registered at the health facility.

*Procedures for PLHIV for whom we will collect routine clinical data.*

We intend to collect demographic and clinical data from patients' medical records that include, but are not limited to: HF, NID, age, sex, level of education, marital status at enrollment in HIV care, date of enrollment in HIV care, date of ART initiation, ARV, Body mass index (BMI), CD4+ T-cell count, HIV-1 viral load (VL) (data and value), WHO clinical stage at the first visit and ART initiation, hemoglobin and full blood count on the date of enrollment in HIV care (or nearest), residence (urban or rural), and records of ART pick-ups (to assess retention) (**Appendix 9**). Data will be extracted from the electronic patient tracking system OpenMRS, that stores clinical information from the medical records of PLHIV registered at the health facility.

**b. Measurement of Results**

**HCW Outcomes:** We will assess the effect of our anti-stigma and resilience training programs on several proposed mechanisms of change among health care workers. These intermediate outcomes, described in **Table 4**, are strongly correlated with improved patient outcomes in large studies around the globe.

**Co-primary outcome - resilience:** We will assess resilience among HCW using Early Warning Resilience Survey. The measure captures data on two subscales (Decompression and Activation) through responses to 8 statements, including, "*I can enjoy my personal time without focusing on work matters*," "*The work I do makes a real difference*," and "*I rarely lose sleep over work issues*."

**Co-primary outcome – HIV stigma:** We will use an assessment of general HIV stigma from the Visser et al. HIV stigma measure validated in South Africa. The general HIV stigma measure includes items from two factors: (i) blame and judgement and (ii) interpersonal/social distancing. **Outcome – anxiety, depression, suicidal ideation:** Depression using the PHQ-9 MZ tool (endline only), anxiety using the GAD-7 (endline only), and suicidal ideation using the Suicide Screening tool (endline only)

**Patient Outcomes:** Our primary measure of effectiveness will focus on patient medication adherence (as measured by proportion of time on medication, see p. 20 for definition), retention (to scheduled clinical appointments and ART pick-ups), and most recent viral load in past 6 months after enrollment (see **Appendix 9**). We will also assess patient outcomes via surveys with PLHIV participants to assess their perception of provider compassion and communication during their clinical visit, as well as how their experience compared with the care they anticipated receiving (based on previous experience and the experience of others in their family/community). The measures used in surveys with patients include Medical Mistrust, Patient Satisfaction, and Perceived Stigma from Health care Providers.

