## 5. Objectives

The overall goal of this project is to assess the impact of two health care worker interventions designed to improve the mental health and well-being of health care workers in Zambézia Province, Mozambique.

Our specific objectives are as follows:

**Objective 1: Evaluate the impact of resilience training only, anti-stigma training only, and resilience and anti-stigma training (vs. standard of care) on hypothesized mechanisms of behavior change among health care workers through a pilot cluster randomized controlled trial (RCT).**

*Hypothesis 1: We hypothesize that health care workers who participate in this training will report a significant reduction in stigmatizing attitudes towards their patients, increased resilience, decreased emotional exhaustion, and decreased depersonalization of their patients.*

**Objective 2: Investigate the impact of health care worker training to reduce stigma and increase wellness and resilience on patient adherence to HIV treatment and satisfaction with health services.**

*Hypothesis 2: We hypothesize that patients receiving care at the site randomized to both resilience and anti-stigma training will have increased adherence to medication (as determined by proportion of time on medication and self-report) at 6 months, higher rates of viral suppression at 6 months, and increased satisfaction at 6 months.*

**Objective 3: Assess experience of moral trauma depression, anxiety and suicidal ideation among health care workers, and explore the perspectives of services/ interventions that could support those at risk of or experiencing moral trauma.**

*Hypothesis: We hypothesize that understanding the experiences and suggestions on mitigating will support development or improvement of interventions that increase wellbeing of health care workers. We will also capture baseline moral injury among health care workers as well as depression, anxiety, and suicidal ideation among health care workers at 10-11 months post intervention.*

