People living with HIV (survey): The study team will recruit participants to complete the baseline and endline surveys at the time the individuals are leaving an appointment for HIV care at one of four eligible health care facilities. Recruitment will be done using convenience sampling when the individual exits the health facility after receiving care. If the individual is interested in participating in the study, a study assistant will bring them into a private room to discuss their eligibility and study procedures (complete surveys at study baseline or endline, i.e., 6 months after the study begins, and to the use of a subset of data from their medical records regarding ART medication pick-up history within the previous 6 months). If eligible and they agree to participate, their informed consent will be obtained by the study assistant at the health facility. Participants can withdraw at any time without impact on the clinical care they are receiving.

People living with HIV who are followed as part of routine care (estimated n=16,000): The study team will not formally recruit and consent these individuals to participate in the study, as only a chart review will be performed. For the inclusion of these individuals' data, we will seek a waiver of informed consent, to be developed and included in the submission to the ethics committees/Institutional Review Board (IRB), to access their retention data and viral load results over the course of the study.

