#### Wellness and Resilience Intervention

Health care workers working at sites randomized to resilience training or the combination anti-stigma and resilience training will receive a group-based Mindfulness-based Wellness and Resilience (MBWR) intervention. The training course will occur every other week and consist of 4 sessions of 60-120 minutes each. The day and time of the intervention session will be determined by health facility staff to facilitate attendance. We will focus on common challenges encountered in the health facility, as well as coping strategies, and future goals to improve provider well-being.

The team selected a group-based, mindfulness-based wellness and resilience (MBWR) intervention. MBWR is designed to be a brief, cost-effective, evidence-based, and replicable intervention to enhance resilience and self-compassion among teams providing primary health care services. The training is based on an established Mindful Practice curriculum^63 and Mindfulness-Based Stress Reduction curriculum. This intervention was selected because it focuses on developing resilience and self-care at the team level (which is how HIV care and treatment is delivered) and because the training can be conducted by a trained Bachelor-level psychologist. The original training course consists of weekly sessions of 60-120 minutes each over 6-10 weeks. Our team has adapted the curriculum to include common challenges encountered in these health facilities, facility-level strategies that can empower health care workers to improve conditions, individual coping strategies, and future goals to improve HCW well-being (see **Table 2**).

**Table 2:** Adapted Wellness and Resilience Training Topics

Focus of Resilience Training Sessions	Intended Learning outcomes
1) Burnout and its consequences and ways to respond/ when to seek care	
 
Factors that may lead to the feeling/ experience of burnout;
 
Understand the signs and symptoms of burn-out and the consequences of not-identified burn-out among health care workers;
 
Getting skills to help colleagues in identifying symptoms;
 
Know how to recognize burnout and where to refer to if experiencing symptoms;
 
Interactive component: share ways that burnout impacts either yourself or colleagues who you work with.
 

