#### Anti-Stigma Intervention

Health care workers working at sites randomized to the anti-stigma only or the combination anti-stigma and resilience arm will receive anti-stigma training sessions to address issues with multiple stigmas that may be impacting their ability to provide quality care for PLHIV in Mozambique. The training will occur once every other week, for at least 4 sessions of 60-120 minutes each. The day and time of the intervention session will be determined by health facility staff to facilitate attendance.

Study personnel will work with health care workers at study sites to combine and adapt the most applicable components from three evidence-based anti-stigma interventions. These interventions were selected because: i) they were developed in low and middle income settings (and parts of one intervention have been tested in Mozambique through International Association of Providers of AIDS Care [IAPAC] modules), ii) their focus is on identifying HIV-related and other intersecting stigmas, the impact stigma has on patients, the impact stigmatized beliefs have on health care providers, and iii) they propose ways to create a stigma-free environment in the health setting (see **Table 3**).

**Table 3:** Adapted Anti-Stigma Sessions

Title of exercise/session	Intended learning outcomes
1. Naming stigma through pictures/defining stigma; describing the different types of stigma; consequences of stigma	
 
Participants discuss what similar stigma takes place in different contexts and start to share stories of what they have personally witnessed.
 
Recognition of how personal attitudes and beliefs influence stigmatizing behavior.
 
Helps participants to recognize the causes of stigma and how the resulting effects are manifested.
 
Interactive component: brainstorming as a group the types of and expressions of stigma in the workplace.
 

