#### **Objective 2:**

With Objective 2 most of our outcomes are continuous measurements, and analyses will be similar to those described above: linear mixed effects models that take advantage of the factorial nature of outcome, with clusters defined as study sites, and unadjusted and adjusted for a small number of PLHIV-level covariates (age, sex, educational level, marital status, language, duration on ART, and history of ART medication pick-ups within the previous 6 months). For binary outcomes (e.g., undetectable viral load), we will fit generalized linear mixed effects models with a logit link function.

Every patient is given 30, 60, 90, or 180 days to pick up their ART medication, as indicated in the medical charts. If a patient picks up medication after the indicated/scheduled date, they will be considered "non-adherent" for each day after their specific pick-up date; this will be assessed over the course of the 6-month follow-up and will be treated as a continuous variable (a proportion between 0 and 1 for each participant). Participants who are lost to follow-up from the health facility during the 6-month follow-up period will be considered "non-adherent" for the days that they are lost. For persons who die or are known to have transferred care outside of the catchment area, the proportion of time on medication will be computed using only time prior to death or transfer of care. For our primary retention outcome (proportion of time on medication), normality assumptions are unlikely to hold, perhaps even after data transformation. Hence, we will fit a cumulative probability model (CPM) with fixed effects for the clinics. The CPM is well-suited for this setting because it does not require symmetry/normality in the outcome (which is bounded between 0 and 1 and likely not normal); in the absence of covariates, it reduces to the Wilcoxon rank sum test. The CPM has been shown to perform well in settings investigating medication adherence. Specifically, the distribution of the proportion of time on medication will be modeled as

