## 15. Timeline

Time (month)	Activities/Description
Month 1	Recruit health care workers from four health facilities (n=100).

Month 1	Among HCW , assess baseline measures of (1) Resilience (2) Stigma (3) Burnout (4) Depersonalization (5) Moral Injury Questionnaire		
Months 1-4	Resilience/Wellness Intervention arm sessions; held bi-monthly	Resilience/Wellness and anti-stigma arm sessions, held bi-monthly	Anti-stigma arm intervention only sessions; held bi-monthly
Months 1-2 & Months 6-7	Recruit a sub-group of PLHIV patients receiving any HIV care and treatment into the study at the four study sites (total n=320) to assess impact of the interventions on medical mistrust, patient satisfaction, and perceived stigma from health care providers via baseline (study start) and end-line (approximately 6 months after study start) surveys.		
Months 1-12	Collect routine clinical data (retention, viral load) from all patients enrolled in care and treatment at the four study sites (n estimated approximately to be 16,000).		
Months 5-7	Among HCW , collect post-intervention surveys (repeat same measures as used at baseline, except for #5 Moral Injury Questionnaire) at all sites (control and intervention).		
Months 8-9	Recruit a sub-group of HCW participants at the three intervention sites for in-depth interviews related to moral injury/ moral trauma.		
Months 8-14	Conduct data analysis of survey outcomes among PLHIV and HCW.		
Months 10-11	Conduct surveys to assess depression, anxiety, and suicidality		
Months 12-15	Conduct data analysis of clinical outcomes among PLHIV.		
Months 12-18	Disseminate findings via community meetings with community members and clinicians		

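### The 6-month patient outcome window has no defined start for the chart-review cohort and, if counted from study start, overlaps the training it is meant to evaluate

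*Combined protocol and SAP*

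**What the plan says.** **Outcome window.** Section 8b lists adherence, retention and viral load as the primary patient measures; the viral load is the "most recent viral load in past 6 months after enrollment". For the proportion of time on medication, section 10 (Objective 2) says only that "this will be assessed over the course of the 6-month follow-up". Hypothesis 2 in section 5 expects "higher rates of viral suppression at 6 months, and increased satisfaction at 6 months".

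**Where the clock starts.** The patient survey is the one place with an explicit origin. Section 7e asks participants to "complete surveys at study baseline or endline, i.e., 6 months after the study begins", and section 8a likewise counts the endline from study initiation. The roughly 16,000 chart-review patients are not recruited (section 7e), so no individual enrollment date exists for them. The first secondary retention measure counts from ART initiation, which is a different origin again.

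**When training happens.** Section 15 places staff recruitment in month 1 and, in its months 1-4 row, "Resilience/Wellness Intervention arm sessions; held bi-monthly", with matching entries for the other two intervention arms. Section 8a gives a different length: "The training course will occur every other week and consist of 4 sessions of 60-120 minutes each" for resilience and "The training will occur once every other week, for at least 4 sessions of 60-120 minutes each" for anti-stigma.

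**What data exist.** The months 1-12 row of section 15 reads "Collect routine clinical data (retention, viral load) from all patients enrolled in care and treatment at the four study sites". Appendix 9 extracts all scheduled and actual pick-up dates and all dated viral loads in the study period. Analysis of clinical outcomes starts in month 12.

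**The concern.** Training cannot affect a pick-up or viral load that precedes it. If the window opens at study start, part of every patient's outcome time is untrained or partly trained care, and this pulls the intervention contrast toward zero.

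The plan handles staff differently. Their follow-up survey in the intervention sites comes within a month of the last session (section 8a), in months 5-7 (section 15). Section 8b treats the staff measures as intermediate steps toward patient benefit, so it is inconsistent to start the patient clock before the staff change is complete.

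At stake are the size of the patient effect carried into the design of the future trial (section 12) and power that is already limited by having four sites. The missing start date is a problem in its own right, because the primary patient outcome cannot be computed without choosing one.

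**Working it through.** **1. The plan's own figure.** Section 7c gives 4,000 patients per facility, ICC 0.05, two-sided 5% and 80% power, with a detectable difference of 0.64 SD. The factorial comparison is two facilities against two.

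- Design effect: 1 + 3,999 × 0.05 = 200.95.
- Effective n per side: 8,000 / 200.95 = 39.8.
- A two-sample t-test on that n gives 0.636 SD. At ICC 0.025 and 0.10 it gives 0.448 and 0.910, against the stated 0.45 and 0.91.

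The figures reproduce and are not in dispute. They contain no allowance for dilution.

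**2. Share of a months 1-6 window before training ends.** Share s = (training end − window start) / window length, with the window starting at study start.

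- Timeline, months 1-4: 4/6 = 67%.
- Four fortnightly sessions from day 1: the last session is at week 6, so 6/26 = 23%. Counting four full fortnights gives 8/26 = 31%.
- Combined arm with its eight sessions one after the other (assumption; the order is not stated): 14/26 = 54% to 16/26 = 62%.

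The share passes one half only if training ends after month 3. Each week of delay before the first session adds 1/26, about 4 percentage points.

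**3. Effect retained in the window average.** Two assumed shapes, both on the mean-difference scale: a step (no effect until training ends) keeps 1 − s; a linear build-up to the end of training keeps 1 − s/2.

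| Training schedule | s | Step | Linear |
|---|---|---|---|
| Four fortnightly sessions from day 1 | 23-31% | 69-77% | 85-88% |
| Months 1-4 | 67% | 33% | 67% |

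**4. What that does to power.** Using the plan's effective n and the normal approximation, power = Φ(d × √(39.81/2) − 1.96), where √(39.81/2) = 4.46. For an undiluted effect of d = 0.64 this gives 81.5%.

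- Months 1-4: d = 0.64 × 1/3 = 0.213 gives about 16% (step); d = 0.64 × 2/3 = 0.427 gives about 48% (linear).
- Four fortnightly sessions: d = 0.64 × 18/26 = 0.443 to 0.64 × 20/26 = 0.492 gives about 51-59% (step); d = 0.64 × 22/26 = 0.542 to 0.64 × 23/26 = 0.566 gives about 68-71% (linear).

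**5. Viral load.** Assume test dates uniform over the window. The most recent of k tests falls before training ends with probability s^k.

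- Months 1-4: 67% for one test, (4/6)² = 44% for two.
- Four fortnightly sessions: 23-31% for one test, (6/26)² to (8/26)² = 5-9% for two.

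The documents give no testing frequency.

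**6. Available alternatives.** Months 5-10 and months 7-12 both fit inside the month 1-12 data collection. If training ends by month 4, neither contains any time before training is complete.

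**The case against.** The strongest reply is that the overlap is inferred. No passage fixes the start of the window for the chart-review cohort, and the study-start origin belongs to the survey. With data to month 12, a later window is not excluded. This stands, and it is why the undefined start is the first part of the point. Study start remains the natural reading, because nothing places the patient clock after training and the staff inclusion criteria refer to a 6-month study period.

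A reader might infer that most of the outcome time precedes full training, or that the estimate is cut to a third. The documents do not support either as a general statement. Both need the months 1-4 row (or sequential delivery in the combined arm), and the one-third figure also needs a step effect. The session schedules in section 8a give a much smaller overlap. Nor can it be said that two thirds of viral loads come before training ends, since the outcome uses the latest result.

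The dilution arithmetic is for a difference in means. The primary adherence model is a cumulative probability model with a log-odds effect, so the percentages indicate order of size and do not transfer directly.

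A later window also has weaknesses. Staff are recruited on a 6-month commitment. Persistence of any effect is untested, and section 10 expects no intervention effect on the late mental-health surveys, although those are different measures. Dispensing of up to 180 days lets medication collected during training cover days after it. These are costs to state and do not remove the overlap.

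Finally, with common calendar dates at all sites, a window from study start is a legitimate estimate of the effect of rolling training out over six months. That is true, but the plan does not say that this is its question.

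**Conclusion.** The point holds in two parts. First, the start of the 6-month patient window is undefined for the chart-review cohort and has to be fixed. Second, if it is study start, the window overlaps training under either schedule in the documents: by about 23-31% for four fortnightly sessions from day 1, and by 67% on the months 1-4 timeline. The effect retained ranges from 33% (months 1-4, step) to 88% (fortnightly sessions, linear). That range rests on an assumed onset shape and a mean-difference scale.

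The overlap dilutes a real effect. It does not create a false one, and it does not make a comparison on common dates invalid. Because the data for a later window are already being collected, the loss is avoidable and the change is worth making. It does not cure the four-site limitation.

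**What to change.** 1. Define the primary patient window by one set of calendar dates applied at all four sites, control included, starting after the last session at the last site to finish (for example months 5-10).
2. Count only viral loads drawn inside that window.
3. Fix cohort membership (adult, active in care) at a common date before training starts, so that selection does not happen after randomization.
4. Report months 1-6 as a secondary analysis, described as the effect over the roll-out period.
5. Reconcile the session schedules in section 8a with the months 1-4 row in section 15, and state how the combined arm's sessions are sequenced.
6. Set all this before patient outcomes are analysed. Appendix 4 already reports staff survey results, so the study appears to be under way and the change should be dated and documented.

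**Cost.** An amendment to sections 8b and 10 and to the 6-month wording of Hypothesis 2. No new data are needed, and a window ending by month 10 precedes the month-12 start of clinical analysis.

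**Downsides to state in the plan.** Staff may leave after their 6-month commitment. The effect may wane. Multi-month dispensing carries over from the training period. With membership fixed before training, patients lost during training enter the window as non-adherent.
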